5 STUDY OBJECTIVES AND ENDPOINTS

5.1 PRIMARY OBJECTIVE

To evaluate the efficacy of oral ferric maltol compared with placebo in the treatment of IDA in subjects with CKD at 16 weeks.

5.2 SECONDARY OBJECTIVE

To evaluate the efficacy, safety, tolerability and pharmacokinetics of ferric maltol in subject with IDA and CKD over a treatment duration of up to 52 weeks.

5.3 PRIMARY ENDPOINT

Change in Hb concentration from baseline to Week 16.

5.4 SECONDARY ENDPOINTS

- Proportion of subjects that achieve an increase in Hb concentration of ≥ 1 g/dL at Week 16.
- Proportion of subjects that achieve a Hb concentration of ≥ 11 g/dL at week 16.
- Change in Hb concentration from baseline to Week 8.
- Proportion of subjects that achieve an increase in Hb concentration of ≥ 2 g/dL at Week 16.
- Change in Hb concentration from baseline to Week 4.
- Changes in iron parameters (ferritin, TSAT, serum iron).
- AEs/SAEs

Additional long-term endpoints up to Week 52/End of Study visit similar to the efficacy and safety endpoints described above.

5.5 PHARMACOKINETIC ENDPOINTS

Population based PK analysis of maltol, maltol glucuronide and serum iron.

5.6 EXPLORATORY ENDPOINTS

Proportion of subjects with a baseline Hb of < 10 g/dL that achieve a Hb > 10 g/dL

6 INVESTIGATIONAL PLAN

6.1 STUDY OVERVIEW

This is a phase 3, randomized, double-blind, placebo-controlled, prospective, multicenter study. Approximately 168 eligible subjects will be randomized at a ratio of 2:1, ferric maltol to placebo.

The study will comprise of the following:

- Screening: Up to 14 days
- Randomized, Double-Blind Treatment: 16 weeks treatment with oral ferric maltol, 30 mg capsule twice daily (bid) or oral matching placebo bid.
- Open-label Treatment: Up to 36 weeks treatment with ferric maltol.
- End of Study: Week 52 or premature discontinuation.
- Post-treatment safety follow-up: 14 days following discontinuation of study medication.

Refer to Section 10 for a schematic of the study design and for details of visits and assessments.

6.2 INVESTIGATIONAL SITES

Approximately 35 sites will participate.

6.3 INCLUSION AND EXCLUSION CRITERIA

No deviations to the inclusion or exclusion criteria are permitted.

6.3.1 Inclusion Criteria

All of the following criteria must be met to randomize a subject in the study:

1. Ability to understand the information given in the Independent Ethics Committee (IEC) or Institutional Review Board (IRB) approved information sheet and consent form. Must sign and date the informed consent and authorization to use protected health information (PHI) in accordance with national and local subject privacy regulations prior to any study mandated procedure.
2. Willing and able to comply with study requirements.
3. Age \geq 18 years at the time of informed consent.
4. A current diagnosis of CKD with an estimated glomerular filtration rate (eGFR) of <60 mL/min/1.73m² and ≥ 15 mL/min/1.73m², as calculated using the abbreviated version of the Modified Diet in Renal Disease equation (MDRD) assessed via screening laboratory results.
5. Iron deficiency anemia defined by the following criteria assessed via screening laboratory results:
 - a. Hb <11.0 g/dL and ≥ 8.0 g/dL
 - b. AND ferritin <250 ng/mL with a Transferrin saturation (TSAT) $<25\%$ OR ferritin <500 ng/mL with a TSAT of $<15\%$
6. Female subjects of childbearing potential (including perimenopausal females who have had a menstrual period within 1 year prior to screening) must agree to use a reliable method of contraception until study completion and for at least 4 weeks following their final study visit. Reliable contraception is defined as a method which results in a low failure rate, i.e., less than

1% per year when used consistently and correctly, such as implants, injectables, some intrauterine contraceptive devices (IUDs), complete sexual abstinence, a vasectomized partner and oral contraceptive medications. Female subjects who are surgically sterile (bilateral tubal ligation, bilateral oophorectomy or hysterectomy) or postmenopausal (defined as no menstrual period within 1 year of screening) are also allowed to participate.

6.3.2 Exclusion criteria

A subject who meets any of the following criteria is not eligible for participation in the study.

1. Anemia due to any cause other than iron deficiency, including, but not limited to:
 - a. Untreated or untreatable severe malabsorption syndrome.
 - b. Myelosuppression use (permitted if taken at a stable dose and frequency for at least 12 weeks prior to randomization and are expected to stay stable throughout the double-blind treatment period so long as there is no clinical evidence of the myelosuppression contributing to the subject's anemia).
2. Administration with any of the following prior to randomization:
 - a. IV iron injection within the previous 4 weeks or administration of intramuscular or depot iron preparation within the previous 12 weeks.
 - b. Single agent oral iron supplementation, taken specifically to treat anemia (e.g. ferrous sulfate, fumarate and gluconate) within the previous 2 weeks. Multivitamins are permitted.
 - c. Use of ferric citrate and sucroferric oxyhydroxide within the previous 1 week.
 - d. ESAs within the previous 4 weeks
 - e. Blood transfusion or donation within the previous 12 weeks.
 - f. Dimercaprol or cloramphenicol within the previous 7 days.
 - g. Current use of methyl dopa.
3. Currently receiving dialysis or initiation of dialysis is considered likely during the study.
4. Renal transplant within 12 months prior to randomization or is considered likely during the study.
5. Known hypersensitivity or allergy to the active substance or excipients of ferric maltol or placebo capsules.
6. Contraindication for treatment with iron preparations, e.g. hemochromatosis, chronic hemolytic disease, sideroblastic anemia, thalassemia, or lead intoxication induced anemia.
7. Impaired liver function as indicated by alanine aminotransferase (ALT) or aspartate transaminase (AST) > 3 times the upper limit of normal as assessed via screening laboratory results.
8. Clinically significant vitamin B12 or folic acid deficiency as determined by the screening laboratory results (retest following at least 2 weeks of starting treatment with vitamin B12 or folate replacement is permitted).

9. Pregnant or breast feeding.
10. Concomitant medical conditions with significant active bleeding likely to initiate or prolong anemia; for example coagulation disorders or recurrent GI bleeding.
11. Scheduled or expected major surgery during the course of the study. (Minor surgeries not associated with significant blood loss, in the Investigator's judgement, are permitted e.g. surgery related to fistulae or vascular access, minor dental extractions, incision and drainage of abscess or simple excisions).
12. Participation in any other interventional clinical study within 30 days prior to screening.
13. Cardiovascular, liver, renal, hematologic, psychiatric, neurologic, gastrointestinal, immunologic, endocrine, metabolic, or central nervous system disease that, in the opinion of the Investigator, may adversely affect the safety of the subject and/or efficacy of the study drug or severely limit the lifespan of the subject.
14. Any other unspecified reason that, in the opinion of the Investigator or the Sponsor make the subject unsuitable for enrolment.

6.4 CONCOMITANT MEDICATION

6.4.1 Not Permitted

- IV iron injections, intramuscular or depot iron administrations.
- Single agent oral iron supplementation, taken specifically to treat anemia (e.g. ferrous sulfate, fumarate and gluconate).
- Ferric citrate or sucroferric oxyhydroxide.
- ESAs.
- Blood transfusions or donations.
- Dimercaprol, chloramphenicol or methyldopa

6.4.2 Permitted

- Myelosuppressants taken at a stable dose and frequency (so long as there is no clinical evidence of the myelosuppressant contributing to the subject's anemia).
- Multivitamins containing iron.

6.4.3 Potential Medication Interactions

As some iron based medications are known to bind to other oral medications and affect absorption, ferric maltol must be administered at least 2 hours before any of these concomitant medications are taken: penicillamine, bisphosphonates, ciprofloxacin, entacapone, levodopa, levofloxacin, levothyroxine (thyroxine), moxifloxacin, mycophenolate, norfloxacin and ofloxacin.

Absorption of both iron and antibiotic may be reduced if oral iron is given with tetracycline. Administration of iron preparations and tetracyclines should be separated by 2 to 3 hours.

Absorption of oral iron may be reduced by calcium and magnesium salts (such as magnesium trisilicate). Administration of iron preparations with such compounds should be separated by at least 2 hours.

6.5 INDIVIDUAL WITHDRAWAL CRITERIA

Subjects have the right to withdraw consent without prejudice at any time during the study. If a subject withdraws consent, the Investigator should make a reasonable effort to determine the cause. All withdrawn subjects should have an End of Study Visit and a follow-up call 14 days after the last dose of study drug (if the subject agrees in the case of withdrawn consent).

Subjects who discontinue study treatment prior to Week 16 will be encouraged to continue with study visits and assessments up to and including assessments at week 16.

Subjects may be discontinued prematurely during the study for the following reasons:

- Withdrawal of informed consent.
- Unwillingness or inability to comply with protocol requirements.
- Pregnancy or not using a reliable method of birth control if female of childbearing potential.
- A ≥ 0.5 g/dL decrease from baseline in Hb that falls below 8.0g/dL on 2 consecutive weeks.
- Ferritin >700 ng/mL with a TSAT of $>50\%$ sustained for 2 consecutive weeks.
- SAEs that are judged by the Investigator to be related to study drug.
- Use of prohibited concomitant medications.
- Initiation of dialysis.
- Blood transfusions or donations for any cause.
- Any dose or frequency changes to myelosuppressants and/or ESAs (greater than 20% over an 8 week period) during the double-blind treatment period.
- Requirement for major surgery. Minor surgeries not associated with significant blood loss, in the Investigator's judgement, are permitted (e.g. surgery related to fistulae or vascular access, minor dental extractions, incision and drainage of abscess or simple excisions).

The reason for study drug discontinuation and the date of last dose should be recorded in the CRF.

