- Open-label Treatment: Up to 36 weeks treatment with ferric maltol.
- End of Study: Week 52 or premature discontinuation.
- Post-treatment safety follow-up: 14 days following discontinuation of study medication.

Subjects that develop a ≥ 0.5 g/dL decrease from baseline in Hb that falls below 8.0g/dL on 2 consecutive weeks will be discontinued from study treatment.

Subjects who discontinue from study treatment prior to Week 16 will be encouraged to continue with study visits and assessments up to and including assessments at week 16.

Number of Subjects

Approximately 168 subjects.

Inclusion Criteria

All of the following criteria must be met to randomize a subject in the study:

1. Ability to understand the information given in the Independent Ethics Committee (IEC) or Institutional Review Board (IRB) approved information sheet and consent form. Must sign and date the informed consent and authorization to use protected health information (PHI) in accordance with national and local subject privacy regulations prior to any study mandated procedure.
2. Willing and able to comply with study requirements.
3. Age ≥ 18 years at the time of informed consent.
4. A current diagnosis of CKD with an estimated glomerular filtration rate (eGFR) of <60 mL/min/1.73m² and ≥ 15 mL/min/1.73m², as calculated using the abbreviated version of the Modified Diet in Renal Disease equation (MDRD) assessed via screening laboratory results.
5. Iron deficiency anemia defined by the following criteria assessed via screening laboratory results:
 - a. Hb <11.0 g/dL and ≥ 8.0 g/dL
 - b. AND ferritin <250 ng/mL with a Transferrin saturation (TSAT) $<25\%$
OR ferritin <500 ng/mL with a TSAT of $<15\%$
6. Female subjects of childbearing potential (including perimenopausal females who have had a menstrual period within 1 year prior to screening) must agree to use a reliable method of contraception until study completion

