via screening laboratory results.

8. Clinically significant vitamin B12 or folic acid deficiency as determined by the screening laboratory results (retest following at least 2 weeks of starting treatment with vitamin B12 or folate replacement is permitted).
9. Pregnant or breast feeding.
10. Concomitant medical conditions with significant active bleeding likely to initiate or prolong anemia; for example coagulation disorders or recurrent GI bleeding.
11. Scheduled or expected major surgery during the course of the study. (Minor surgeries not associated with significant blood loss, in the Investigator's judgement, are permitted e.g. surgery related to fistulae or vascular access, minor dental extractions, incision and drainage of abscess or simple excisions).
12. Participation in any other interventional clinical study within 30 days prior to screening.
13. Cardiovascular, liver, renal, hematologic, psychiatric, neurologic, gastrointestinal, immunologic, endocrine, metabolic, or central nervous system disease that, in the opinion of the Investigator, may adversely affect the safety of the subject and/or efficacy of the study drug or severely limit the lifespan of the subject.
14. Any other unspecified reason that, in the opinion of the Investigator or the Sponsor make the subject unsuitable for enrolment.

Concomitant Medication

Not Permitted

- IV iron injections, intramuscular or depot iron administrations.
- Single agent oral iron supplementation, taken specifically to treat anemia (e.g. ferrous sulfate, fumarate and gluconate).
- Ferric citrate or sucroferric oxyhydroxide.
- ESAs.
- Blood transfusions or donations.
- Dimercaprol, chloramphenicol or methyldopa

Permitted

- Myelosuppressants taken at a stable dose and frequency (so long as there is no clinical evidence of the myelosuppressant contributing to the subject's anemia).
- Multivitamins containing iron.

Withdrawal Criteria

- Withdrawal of informed consent.
- Unwillingness or inability to comply with protocol requirements.
- Pregnancy or not using a reliable method of birth control if female of childbearing potential.
- A $\geq 0.5\text{g/dL}$ decrease from baseline in Hb that falls below 8.0g/dL on 2

consecutive weeks.

- Ferritin >700ng/mL with a TSAT of >50% sustained for 2 consecutive weeks.
- SAEs that are judged by the Investigator to be related to study drug.
- Use of prohibited concomitant medications.
- Initiation of dialysis.
- Blood transfusions or donations for any cause.

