4.5.1 Study Population

Adult subjects will be enrolled who have a diagnosis of CKD with an eGFR of < 60 and at least $15 \text{ mL/min/1.73m}^2$. It is anticipated that this population will in general have less significant renal disease and comorbidities and be better able to tolerate the placebo phase of the study. Subjects will also have IDA as defined by Hb, ferritin and TSAT levels. Subjects should not be severely anemic and so will have $\text{Hb} \geq 8.0 \text{ g/dL}$. Subjects who have recently received IV iron, a blood transfusion or renal transplant will not be permitted to enter the study.

All subjects entering this study will be anemic ($\text{Hb} < 11.0 \text{ g/dL}$) which falls below the lower limit of normal Hb (13.5 g/dL for males, 12.0 g/dL for females per KDOQI 2006) for investigational purposes since the benefits to subjects being treated with ferric maltol with a Hb between 11 g/dL and the lower limit of normal could be marginal. Additionally, the cut-off of 11.0 g/dL is in line with KDOQI 2006 who specify a target Hb level of 11 g/dL or greater.

The inclusion criteria of $< 250 \text{ ng/mL}$ ferritin with a $< 25\%$ TSAT and or a $< 500 \text{ ng/mL}$ ferritin with a $< 15\%$ TSAT is indicative of iron deficiency and representative of the population likely to benefit from iron treatment.

Subjects who develop Hb concentration decreases of $\geq 0.5 \text{ g/dL}$ from baseline that falls below 8.0 g/dL

on 2 consecutive weeks will be withdrawn from the study and corrective measures implemented outside of the study. Withdrawal from the study would also be possible based on any AE, including anemia related symptoms, which the Investigator deemed significant. There is little data available on long or medium term Hb changes in CKD placebo treated subjects, so it is not possible to accurately predict how many subjects may have to withdraw during the 16 week placebo controlled period. However a study looking at ESA treatment in over 2000 anemic, CKD diabetic patients followed for 2.3 years showed that 55% of patients on placebo and without ESA treatment maintained a Hb >9.0 g/dL and that on average, Hb levels were either stable or increased in both the active and placebo groups (Skali 2013). The Hb decline in this study is not reported separately for hemodialysis and non-dialysis subjects, nor by iron replete or deficient subjects, however over a 2 year period the Hb decline did appear slow for most patients.

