4.6 RISK-BENEFIT EVALUATION

KIDGO recommends initiating treatment for IDA with oral ferrous products which are associated with GI side effects. If unsuccessful IV iron administration should be considered (see section 5.2).

This is in accordance with the labelled warnings of marketed oral iron products. The Summary of Product Characteristics (SPCs) for the various OFPs which warn that oral iron salts may have a corrosive effect that may exacerbate the symptoms associated with certain GI disease states such as peptic ulcer disease or IBD (e.g., UC). But despite this warning there are limited comparative data from prospective clinical trials investigating the AE profile of marketed oral iron products as compared to placebo or active comparators or comparing IBD to different patient populations.

The dose chosen for the Phase 3 development program, 30 mg bid, has been shown to be effective and well-tolerated in IDA patients with IBD for up to 64 weeks of treatment. In contrast to other marketed iron products, in particular ferrous drugs, the sugar derivative maltol strongly chelates iron, stabilizes iron in the less toxic ferric (Fe³⁺) form and renders it readily available for absorption in the intestinal tract. Consequently, the frequency of typical adverse effects is hypothesized to be reduced with administration of ferric maltol. This hypothesis is confirmed by ferric maltol being well-tolerated in patients who are intolerant to oral ferrous products in clinical studies ST10-01-301 and ST10-01-302; furthermore, unlike oral ferrous products, ferric maltol did not increase flare of underlying disease in these patients compared to placebo treatment.

The current study design does not pose additional risk for the subjects as no additional interventional procedures are planned during the study period, except for blood sampling similar to clinical routine. The patients randomized to placebo will be monitored and withdrawn should the

Hb fall ≥ 0.5 g/dL from baseline that falls below 8.0g/dL on 2 consecutive weeks.

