The intervals of Hb measurement within the schedule of study visits fall within KDOQI guidelines on monitoring Hb in patients receiving iron replacement. All patients who complete the randomized phase and remain on-treatment will enter an extended open-label phase of ferric maltol treatment and potentially benefit from iron replacement. The safety profile of ferric maltol as established from completed studies is considered acceptable and therefore the overall benefit/risk to subjects entering this study is also acceptable.

Refer to the Investigator's Brochure for further details on risk/benefit assessment.

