8.4 EMERGENCY UNBLINDING

Under normal circumstances, the blind should not be broken. The blind should be broken only if specific emergency treatment would be dictated by knowing the treatment status of the subject. It is highly unlikely that this situation will occur during this study. In such cases the Investigator can break the blind via the IXRS/randomization system. The system will encourage the Investigator to discuss the situation with Sponsor prior to breaking the code. Un-blinding will result in discontinuation of the subject from the study treatment and withdrawal from the study.

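### The Hb stopping rule needs low values on 2 consecutive weeks, but no required sample can confirm a first low value in that time, and Section 4.5.1 conflicts with the synopsis on whether such subjects leave treatment or the study

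*Combined protocol and SAP*

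**What the plan says.** **The rule.** The Hb condition appears in the synopsis (Design and Withdrawal Criteria) and in Sections 4.5.1, 4.6 and 6.5. Each statement has the same two parts: a fall of at least 0.5 g/dL from baseline, and Hb under 8.0 g/dL on two consecutive weeks. Section 6.5 words it as a "decrease from baseline in Hb that falls below 8.0g/dL on 2 consecutive weeks".

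**Sampling.** In Section 9.2, double-blind hematology is required at screening, randomization and Weeks 4, 8 and 16. Week 12 is by telephone. A note under the table says that unscheduled visits may be needed and gives repeat laboratory sampling as an example. Section 9.8 has the investigator review each result and grade out-of-range values as clinically significant or not.

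**What happens to the subject.**
- The synopsis (Design) says that subjects with the defined fall "on 2 consecutive weeks will be discontinued from study treatment".
- Section 4.5.1 says that they "will be withdrawn from the study and corrective measures implemented outside of the study".
- Section 4.6 begins "The patients randomized to placebo will be monitored and withdrawn should the" and then repeats the Hb condition, without saying what the subject is withdrawn from.
- Section 6.5 says that subjects who stop treatment before Week 16 "will be encouraged to continue with study visits and assessments up to and including assessments at week 16". The synopsis and the Section 9.2 footnote carry the same sentence.

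**Other routes and context.** Section 4.5.1 also allows withdrawal for any adverse event that the investigator considers significant, including symptoms of anemia. On visit spacing, Section 4.6 states: "The intervals of Hb measurement within the schedule of study visits fall within KDOQI guidelines".

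**The concern.** Section 4.6 presents this rule as the protection for placebo subjects, who may enter with Hb as low as 8.0 g/dL. A rule that depends on two values about a week apart needs a second sample at about that time. If none is prescribed, whether a subject stops depends on whether the site chooses to resample. With about 35 sites, the same Hb could stop one subject and leave another on blinded treatment.

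The second issue concerns the primary endpoint, change in Hb to Week 16. A subject who stops treatment but stays in follow-up can still supply that value. A subject who leaves the study cannot. Those affected would be selected because their Hb was falling, so their missing values would not be a random subset.

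**Working it through.** The plan gives no figure for how many subjects would meet the rule, so there is none to reproduce. The check compares the rule with the schedule, and then the consequence statements with one another.

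**1. Can required samples meet the rule?** The inputs are the visit weeks and the two windows printed in Section 9.2 (±3 and ±7 days). The column spans did not survive conversion from PDF, so three readings are shown. Shortest gap = nominal days minus the two windows.

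| Pair of samples | Nominal | ±3 days throughout | ±3 at Weeks 4 and 8, ±7 at Week 16 | ±7 days throughout |
|---|---|---|---|---|
| Week 4 to 8 | 28 | 28 − 3 − 3 = 22 | 28 − 3 − 3 = 22 | 28 − 7 − 7 = 14 |
| Week 8 to 16 | 56 | 56 − 3 − 3 = 50 | 56 − 3 − 7 = 46 | 56 − 7 − 7 = 42 |

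The randomization sample is drawn before the first dose. Even if it were counted, its shortest gap to Week 4 is 28 − 7 = 21 days.

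Two samples a week apart are separated by 7 days. On the loosest reading, two days in adjacent calendar weeks are at most 13 days apart. The smallest entry in the table is 14 days, so no pair of required double-blind samples meets the condition.

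In the open-label period, samples fall at Weeks 16, 24, 32, 42 and 52. The gaps there are 8, 8, 10 and 10 weeks.

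**2. Does other text supply the second sample?**
- The Section 9.2 note permits a repeat. It has no trigger, no interval and no link to Hb under 8.0 g/dL.
- Section 9.8 requires review and grading of results, not a repeat.
- Under Section 10.1.1, an abnormal laboratory value becomes an adverse event only if judged clinically significant. Expected progression of the studied disease, including its laboratory values, is excluded unless more severe than expected. Follow-up of events in Section 10.2 has no interval.
- The significant-adverse-event route in 4.5.1, with adverse events also collected at the Week 12 call, can reach a subject with symptoms. It does not ensure a recheck in one without symptoms.

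So an asymptomatic first crossing at Week 8 has no required recheck for a nominal 8 weeks.

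**3. Is the wording conflict one of substance?** Section 8.4 names both outcomes in one sentence: "Un-blinding will result in discontinuation of the subject from the study treatment and withdrawal from the study". The Section 9.2 footnote also gives separate instructions for subjects who withdraw from the study and for those who stop treatment. The two phrases are therefore not interchangeable here.

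Under 4.5.1, a subject confirmed before Week 16 would have the Week 16 procedures at withdrawal (Section 9.2 footnote). The actual Week 16 Hb would be missing and would go to the multiple imputation in Section 11.2.1, which uses baseline, Week 4 and Week 8 Hb and gender. Under the synopsis, the actual value may be obtained.

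**The case against.** The strongest reply is that the plan is workable as it stands. A rule written in weeks, beside a note naming repeat sampling as a reason for an unscheduled visit, implies a follow-up draw. Investigators see every result, and symptoms are a separate ground for withdrawal. Use of IV iron or an ESA, or a transfusion, is another. Section 4.5.1 also cites a placebo-treated CKD cohort in which Hb was on average stable or rising and decline appeared slow for most patients, with stated limits on subgroup reporting. On the second issue, 4.5.1 is rationale text, the operative sections already carry the retention sentence, and imputation would use the subject's earlier Hb values.

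Much of this stands. A reader might infer that placebo subjects are unprotected, or that the rule can never be applied. The documents do not support either: repeats are allowed and symptomatic decline has its own route. Nor do they show that visits are too far apart, since Section 4.6 places the routine spacing within KDOQI guidance. The gap is the missing confirming sample.

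What the reply does not supply is a trigger or an interval for an asymptomatic low Hb, or a single stated consequence. The Central Laboratory Manual was not available. Section 9.8 cites it for sample collection and processing.

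**Conclusion.** The point holds on both parts. Required double-blind samples cannot meet the Hb rule on any reading of the windows, and nothing requires or times the repeat that would. Section 4.5.1 and the synopsis prescribe different outcomes for the same subject. Section 4 is what needs changing, because the synopsis, Section 6.5 and the Section 9.2 footnote all provide for follow-up to Week 16.

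The size can be stated only as time: 4 or 8 weeks nominally between required samples, against about 1 week implied by the rule. Section 4.5.1 itself says that the number of withdrawals cannot be accurately predicted. A reader might go further and infer a biased primary result or a loss of power. The documents do not allow either to be estimated. Counts of crossings would rest on assumed baseline distributions, mean changes and SDs at Weeks 4 and 8, so none are given. Retention is also not a complete remedy, since an Hb taken after corrective treatment may reflect that treatment.

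A reader might extend the point equally to the iron-overload rule, "Ferritin >700ng/mL with a TSAT of >50% sustained for 2 consecutive weeks". It too has no timed repeat, but its wording could be read as satisfied by two successive scheduled values, so that case is weaker.

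**What to change.** 1. In Sections 6.5 and 9.2, require a repeat Hb about 7 days after a first value under 8.0 g/dL with a fall of at least 0.5 g/dL from baseline. Apply this in both arms, because sites are blinded. The rule is met if the repeat confirms the finding. The 7-day interval is chosen to match the rule's own wording.
2. In Sections 4.5.1 and 4.6, say that such subjects stop study treatment and are encouraged to continue assessments to Week 16, as the synopsis, Section 6.5 and the Section 9.2 footnote already provide.
3. Optionally, add a timed repeat for the ferritin/TSAT rule.

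No separate item on recording rescue treatment is needed, since Section 9.5 already documents medication changes and procedures throughout the study.

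The cost is amendment wording and one extra blood sample for each subject who crosses the threshold, in either arm and also in the open-label period. Some stops that would otherwise go unconfirmed will be confirmed. No extra routine visits are needed.
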